All data collected by a research assistant on site will be transported from TLH to the CASAA research offices in a briefcase or similar closed storage medium—loose papers or papers in open folders will not be allowed. After returning to the research office, all hard copy data will be stored in a locked file cabinet. Audio recordings will immediately be transferred onto a computer and deleted from the digital recorder. All computerized data (including audio recordings) will be stored on the CASAA server, which is firewall protected, and accessible only through individual authorization and passwords. Audio recordings will be reviewed in closed rooms at the lowest reasonable volume or with headphones. Data will be retained for publication purposes for five years following the last study publication, per usual data retention standards.

Data collected from this project will be available only to selected research staff. Data will be collected by research staff and shared with treatment staff only if there is a need in order to protect patient or family member safety. For example, if during the baseline assessment a research staff member finds out that a participant has current suicidal ideation, we would share this with a clinician because this could have material effect on the participant's well being. Other than those contingencies only the research staff composed of the research assistants, co-investigators and the PI will have continuing access to participant data. Similarly, disclosures of child abuse or neglect will, by law, be reported to the CYFD.

II. Data Analysis/Statistical Considerations

Statistical power. The R34 mechanism is developmental in nature and for this reason substantial emphasis in this application is placed upon both inferential testing and the estimation and evaluation of effect sizes. Our test of the efficacy of the B-FIT intervention after anticipated attrition (15%; Aim 2a) will include 34 participants in the B-FIT group and 17 in TAU and test outcomes both for

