Cross-level interactions will be tested via the *t*-statistic to identify potential time by group interactions in changes in alcohol use. Type I error will be adjusted to $\alpha = .05/2 = .025$ to account for the correlation between PDA and PDH.

Aim 2c. This aim will investigate whether the relative benefit of B-FIT occurred for the presumed reasons. As such, this aim will focus only on participants assigned to the B-FIT group ($n = 40$ at baseline). Tests of mediation will use a product-of-coefficients approach with a bootstrapping procedure (Hayes, 2009). This choice provides the most powerful test of mediation with smaller samples and does not assume normality in the distribution of ($a'b'$) product terms (Preacher and Hayes, 2008; Hayes, 2009). Three active ingredients of B-FIT will be investigated separately: (1) teaching skills to reinforce change, (2) teaching skills to increase positive exchanges, and (3) teaching skills to improve communication, all of which are measured within treatment by the modified C-TIRS. Baseline values of mediators will be entered into all planned analyses as covariates. Overall, we will conduct six mediational tests. First, we will conduct 3 mediational tests to evaluate our prediction that teaching skills to reinforce change will increase 4-month abstinence (PDA) by mobilizing three mediators during the treatment phase of the study (TAU treatment adherence, commitment to abstinence, and perceived family support). The fourth test will examine if teaching skills to reinforce change increases family satisfaction (month 4) through enhanced impressions of perceived family support (within treatment). Our fifth test will examine if teaching skills to enhance positive family exchanges produces increased family satisfaction (month 4) by increasing positive shared time (within treatment). Finally, we will assess if teaching skills to improve communication increases 4-month family relationship satisfaction by mobilizing more positive partner communications within treatment. No adjustment for inflated Type I error is planned for these six tests.

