Two post hoc strategies will be used to assess the confidence we can place on the results of our unprotected tests. First, we will employ a multiple mediational model (Hayes, 2009) to examine the actions of one B-FIT active ingredient, teaching skills to reinforce change. Here, if two or more of the mediators linked with this active ingredient are found to be significant in the primary analyses we will enter those mediators into a single multiple mediation model. Although this approach lacks the precision of the primary analyses, it does address the concern of potential mediator multicollinearity and the likely erroneous rejections of null hypotheses. Second, we will descriptively assess the magnitude and consistency of *a* and *b* path estimates generated in our primary mediational analyses. Using meta-analytic techniques, for example, we will determine if the *a* ($n= 5$) and *b* ($n=6$) path parameter estimate distributions are homogeneous or not using the *Q* statistic (Borenstein, Hedges, Higgins, & Rothstein, 2009). We believe that the rejection of the assumption of homogeneity will provide important descriptive information in the identification of “key signals” or actions among the active ingredients and presumed mediators.

Aim 2d. Moderators of B-FIT Response. Three classes of moderators will be collected at the intake interview and examined in these exploratory analyses: (1) demographic variables, (2) psychological variables, and (3) familial distress/support, such as perceived social support from family. Primary interest will focus on the moderating effect of these variables on monthly PDA and PDH while secondary analyses will assess the extent to which these moderators influence family relationship satisfaction. All moderators will be binary, and we will use median splits on continuous moderator variables to generate groups with equal number of patients, e.g., patient age. Two longitudinal HLM growth models will assess potential moderating effects of patient characteristics on treatment effectiveness using PDA and PDH. Baseline value of the dependent measure will be entered as a covariate and monthly PDA and PDH will be the dependent measure in the hierarchical linear model. The time effect will be restricted to the linear term and a given moderator variable will be entered in level two of the model. Additional terms entered in level 2 of these models will include a dummy coded

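### The multiple-mediator check for the reinforce-change ingredient is gated on significance in the same data, so a correlated mediator with no effect of its own can stand alone, unadjusted, when the real one is missed

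*Combined protocol and SAP*

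**What the plan says.** The passages are in the Combined protocol and SAP, STUDY DATA, section II (Data Analysis/Statistical Considerations), Aim 2c.

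- **Sample.** The aim uses the B-FIT arm only, 40 patients at baseline. The power paragraph expects 34 of them after 15% attrition.
- **Method.** "Tests of mediation will use a product-of-coefficients approach with a bootstrapping procedure". No significance or confidence level is stated for these tests.
- **Mediators.** The reinforce-change ingredient is predicted to raise month-4 PDA through "three mediators during the treatment phase of the study (TAU treatment adherence, commitment to abstinence, and perceived family support"). Each is tested in its own model.
- **Multiplicity.** "No adjustment for inflated Type I error is planned for these six tests".
- **First post hoc strategy.** For this ingredient, "if two or more of the mediators linked with this active ingredient are found to be significant in the primary analyses", then "we will enter those mediators into a single multiple mediation model". The plan concedes that this model is less precise than the primary analyses, but says that "it does address the concern of potential mediator multicollinearity and the likely erroneous rejections of null hypotheses".
- **Second post hoc strategy.** The a and b path estimates are reviewed descriptively and tested for homogeneity with the Q statistic. This does not depend on significance.

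**The concern.** A mediator with no effect of its own can look real because it is correlated with a real mediator that was left out of its model. The remedy is to adjust for the real one, whether or not that one reached significance. The plan's gate makes the adjustment depend on significance. In a sample of about 34 the real mediator is often missed. If its correlate is then the only one declared, the gate stays shut and nothing separates the two.

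At stake is how far a single significant mediator can be trusted as evidence of mechanism. The plan credits this model with handling that problem, and the model is absent in some of the cases where the problem arises.

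**Working it through.** **1. The plan's own figure.** 40 × (1 − 0.15) = 34, as stated. The plan gives no operating figure for the mediator check, so the rest needs assumptions.

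**2. Model (assumed).** Standardised ingredient score X. Mediators Mj = aX + √(1 − a²)·ej for j = 1, 2, 3, with correlation r between the residuals ej. Outcome PDA = b·M1 + √(1 − b²)·u. M1 is real; M2 and M3 respond to X but do not affect PDA. The runs take a = b, with r of .3 and .5.

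**3. Why a false mediator is declared.** Given X, the slope of M1 on M2 is r. So M2's b path in its own model is b × r although its true value is 0. At a = b = .39:

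- r = .3: .39 × .3 = .117, so the apparent indirect effect is .39 × .117 = .046.
- r = .5: .39 × .5 = .195, so it is .39 × .195 = .076.
- Real mediator: .39 × .39 = .152.

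In a model that includes M1, M2's b path is 0.

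**4. How often the gate stays shut.** The simulations use n = 34. A false declaration means that M2 or M3 is significant in its single-mediator test; no check runs if only one of the three mediators is significant. The first two result columns use joint significance of a and b (5% each) as a proxy for the bootstrap, and the second of these is a larger repeat with 20,000 trials per setting. The last column uses a percentile bootstrap with a 95% interval, at paths .3, .4, .5 and .6. Each cell gives r = .3, then r = .5.

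| Paths a = b | No check, given a false declaration | Same, 20,000-trial repeat | Same, percentile bootstrap |
|---|---|---|---|
| .3 | 72%, 55% | 72%, 60% | 71%, 67% |
| .39 (.4) | 48%, 34% | 47%, 38% | 49%, 38% |
| .5 | 23%, 18% | 20%, 16% | 20%, 14% |
| .59 (.6) | 8%, 6% | 9%, 6% | 10%, 6% |

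The three runs agree within simulation error. At n = 40 the bootstrap shares are lower: 65% and 49%, 38% and 30%, 15% and 10%, 5% and 4%. The share falls as paths grow because the real mediator is then usually detected. Its single-test power is about .15 at paths .3, .35 at .39, .67 at .5 and .85 at .59.

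**5. Share of all trials.** Multiply by the chance of any false declaration. At paths .39, joint significance:

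- r = .3: .106 × .48 = 5.1%.
- r = .5: .182 × .34 = 6.2%.

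Across path sizes the range is about 2-6%; the repeat puts the top at .186 × .376 = 7.0%. The bootstrap runs give from .271 × .10 = 2.7% (paths .6, r = .3) to .207 × .38 = 7.9% (paths .4, r = .5). If M2 and M3 do not respond to the ingredient (a = 0 for them), a false declaration occurs in only about 1-2% of trials, and an unchecked one in under 1%.

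**6. The check runs without the real mediator.** This happens in a further 1-6% of false declarations (up to 9% with the bootstrap).

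**7. Effect of removing the gate.** Suppose a mediator must hold both in its single test and in an always-fitted three-mediator model. At paths .39, the chance that a false mediator stands falls from 6.1% to 3.2% (r = .3) and from 7.7% to 3.4% (r = .5). The gain is smaller at larger paths: in the repeat, 5.7% to 4.5% at paths .59, r = .3.

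**Limits.** Baseline mediator covariates were left out. It is also unclear whether perceived family support, which has a second test on family satisfaction, could meet the gate through that test.

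**The case against.** **Size.** The documents give no path sizes or correlations. With large paths the gate rarely matters, and even at small ones an unchecked false mediator is a matter of a few percent of trials. This stands, and it is why the result is given as a range. A reader might infer that the safeguard is usually missing when needed; that holds only for small paths.

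**Candour.** The plan calls the tests unprotected and the checks post hoc, and describes the grant as developmental. That stands too, but the plan still says this model addresses erroneous rejections.

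**No check at all.** A reader might infer that a lone mediator faces no scrutiny. The documents do not support that, because the Q-statistic strategy always runs. It does not, however, adjust one mediator for another.

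**Consequence.** A reader might infer that a wrong mechanism would be carried into the larger trial. Aim 3 lists manuals, training materials, an integrity rating system and measures, and nothing in the plan makes these depend on which mediator is significant.

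**All mediators real.** One could add that the check may also fail to run when all three mediators are real. No erroneous rejection exists in that case, so it does not support the point. Nor does the point rest on any inflation of the estimates that pass the gate, which has not been quantified.

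**Precision.** With about 34 patients, limiting the joint model to mediators that have already shown a signal is a defensible choice. This is the strongest objection. It argues against replacing the single-mediator tests, but not against reporting the full model beside them.

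**Conclusion.** The point holds as a minor one. The gate is explicit, uses the same data, and can leave a correlated false mediator without the adjusted check that the plan credits with guarding against it. At n = 34 this affects about 55-72% of false declarations at paths .3, 34-48% at .39, 18-23% at .5 and 6-8% at .59. That is about 2-6% of all trials by the joint-significance proxy and 3-8% by percentile bootstrap.

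These figures assume one real mediator, two false ones that respond to the ingredient, and residual correlations of .3 to .5. If the false ones do not respond to the ingredient, the problem all but disappears (under 1% of trials). The mechanism follows from the plan's text; its frequency rests on assumptions the documents cannot settle.

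**What to change.** Keep the three single-mediator tests as planned. Remove the condition that two or more be significant. Always fit, as a supplementary analysis, one model with adherence, commitment and perceived family support together, and report each specific indirect effect with its bootstrap interval and the stated level. Report a mediator as supported with more confidence when it holds in both analyses.

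The model should supplement the single tests, not replace them. Used alone, it declares a false mediator in about 8-12% of bootstrap trials at paths .5 to .6, no better than the 7-9% under the present plan.

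The change needs only SAP wording, since the measures and the model are already planned. The statistical cost is wider intervals. At paths .39, power for a single real mediator falls from about .35 in its own test to about .29 (r = .3) or .24 (r = .5) in the joint model. If all three are real and correlated, the loss is larger: about .48 to .26 at r = .3, and .57 to .22 at r = .5. The SAP should therefore say that non-significance in the joint model is lack of confirmation, not refutation.

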variable representing treatment assignment and a product term reflecting the group assignment by moderator interaction. *We acknowledge that the exploratory analyses in Aim 2d are statistically underpowered and involve substantial inflated Type I error.* In this light we are especially interested in the “pattern” of statistically significant findings in our moderator analyses rather than in a single inferential test.

III. *Quality Control and Quality Assurance*

Treatment fidelity. To measure treatment fidelity to ABCT, the PI and colleagues developed the 37-item Couples Treatment Integrity Rating Scale (C-TIRS (Hallgren et al., under review). Because ABCT includes interventions not relevant to B-FIT, the C-TIRS will be shortened to eliminate CBT items; other items will be reworded to assess interventions with family member rather than just an intimate partner. Sessions will be digitally recorded and rated for fidelity by graduate students trained to use the modified C-TIRS, using training and reliability procedures used previously in our lab.

Therapist selection, training, and supervision. B-FIT therapy sessions will be provided by a TLH clinician. Clinician training will include four elements: (a) didactic material on the rationale for B-FIT and each B-FIT intervention as well as a detailed description of each intervention; (b) role play rehearsal of each intervention; (c) supervised practice with the B-FIT manual with the first six patients/CFMs in which each audio-taped session will be reviewed by [name], or [name] and feedback provided to the clinician; (d) additional didactic training and role play rehearsal with the modified B-FIT protocol after the pilot testing and second round of focus groups. Treatment delivery will be monitored throughout the small clinical trial and Drs. [name], [name], and [name] will continue to listen to session tapes and give feedback to study clinicians.

Data quality assurance. PES has established standards for tracking data collection and quality. PES staff will review a checklist for each participant, verifying that they have completed all appropriate assessments and procedures. Regulatory binders will be created as a reference and updated on an ongoing basis to reflect any revised measures and consent forms. Assessments will be entered into the database twice by separate individuals, and the PES director will do monthly checks to identify and resolve any discrepancies in data entry.

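### Aim 2d median-splits every continuous moderator only to equalise group sizes; keeping them continuous is a cheap, minor gain in precision if moderation is roughly linear

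*Combined protocol and SAP*

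**What the plan says.** **Moderators.** Under Data Analysis/Statistical Considerations, Aim 2d, the plan states: "All moderators will be binary, and we will use median splits on continuous moderator variables to generate groups with equal number of patients". Patient age is the example given. Each moderator enters level two of a growth model for PDA or for percentage of days of heavy drinking (PDH), together with treatment and their product. The plan is frank about the status of this work: "We acknowledge that the exploratory analyses in Aim 2d are statistically underpowered and involve substantial inflated Type I error". It will look at the pattern of "statistically significant findings in our moderator analyses rather than in a single inferential test". No alpha is set for Aim 2d. The Statistical power paragraph says that "substantial emphasis in this application is placed upon both inferential testing and the estimation and evaluation of effect sizes", and that the efficacy analysis "will include 34 participants in the B-FIT group and 17 in TAU".

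**Mediation.** In Aim 2c, "this aim will focus only on participants assigned to the B-FIT group". Tests 1 to 3 have 4-month PDA as outcome, with TAU adherence, commitment to abstinence and perceived family support as mediators. The covariate rule is: "Baseline values of mediators will be entered into all planned analyses as covariates". Baseline PDA is neither named nor excluded. Elsewhere the plan does adjust for baseline drinking: in the Aim 2a drinking models, in the adherence model, and in Aim 2d ("Baseline value of the dependent measure will be entered as a covariate and monthly PDA and PDH will be the dependent measure").

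**The concern.** Equal halves are not a statistical reason to cut a continuous variable. A product of treatment and the continuous moderator uses all the information, whereas a split treats patients just either side of the median as different and everyone within a half as alike. The split does not secure equal cells where they matter either: halving 34 and 17 gives expected cells of 17 and 17 in B-FIT but only 8.5 and 8.5 in TAU, and balance within arm is not guaranteed. The cost is a wider interval for each interaction, in a study that puts weight on estimating effect sizes and already has few patients. Naturally binary moderators are not affected.

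The mediation point is separate and smaller. Within one arm, the path from mediator to outcome is not protected by randomisation. If baseline PDA predicts both the mediator and 4-month PDA, leaving it out can bias that path; if it predicts only the outcome, leaving it out loses precision. The plan itself links baseline PDA to a mediator only for adherence (test 1). For commitment and perceived support the link is an assumption.

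**Working it through.** The plan states no power or precision figure for Aims 2c or 2d, so there is none to reproduce.

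**Inputs from the plan.** B-FIT 40 at baseline and 15% attrition: 40 × 0.85 = 34. TAU 17. Total 51.

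**Assumed, because the plan gives nothing.** Outcome SD 1; correlation of baseline with outcome .5; two-sided .05; slopes in outcome SD per moderator SD; all correlations in the mediation check.

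**1. Large-sample limit.** For a normal moderator with linear moderation, a median split keeps 2/π = .637 of the information (.75 for a uniform moderator). 51 × .637 = 32.5.

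**2. At the actual sample size.** Least squares with arm, moderator, baseline covariate and product, 34 versus 17, 20,000 simulated trials per slope. The split estimate is divided by 1.596, the expected gap between half means, to put it on the same scale.

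- Mean 95% interval width at slopes 0.1 to 0.2: 1.12 continuous versus 1.33 to 1.34 split. The ratio is about .84, so about 16% narrower (11% for a uniform moderator).
- Retained information at slope 0.1: .842² = .709, and 51 × .709 = 36.2. Variance ratios of .71 to .73 at slopes 0 to 0.3 give 36 to 37 patients.

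| Slope | Power, continuous | Power, split |
|---|---|---|
| 0 | .049 | .047 |
| 0.1 | .06 | .06 |
| 0.2 | .12 | .09 |
| 0.3 | .19 | .14 |
| 0.5 | .43 | .28 |

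A repeat run gave .42 versus .28 at slope 0.5. Using the mean of four monthly values (assumed intraclass correlation .5), power is .15 versus .11 at slope 0.2 and .61 versus .41 at 0.5. The error rate per test stays near 5% under either coding.

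**3. When moderation is not linear on the scale entered** (power, continuous versus split):

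- Step at the median of 0.4, 0.6 or 1.0 SD: .09 versus .10, .14 versus .16, .29 versus .37.
- Saturating effect (tanh of twice the moderator, scaled to SD 1): .17 versus .17 at size 0.3, .37 versus .36 at 0.5.
- Lognormal moderator (log SD 1.5), effect linear in the log, entered untransformed: .127 versus .140 at 0.3, .25 versus .28 at 0.5. At log SD 1 the two are close (.30 versus .28 at 0.5).

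**4. Mediation tests 1 to 3.** n = 34, true b = 0, percentile bootstrap of the product a × b as planned, baseline PDA and baseline mediator correlated .3, baseline mediator and mediator correlated .5. False-positive rate without versus with baseline PDA:

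| PDA–mediator / PDA–outcome correlation | a = 0 | a = .2 | a = .4 |
|---|---|---|---|
| .3 / .3 | .006 vs .004 | .016 vs .011 | .054 vs .048 |
| .3 / .5 | .005 vs .004 | .020 vs .009 | .068 vs .044 |
| .5 / .5 | .009 vs .002 | .050 vs .014 | .190 vs .052 |

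In the corner case of .5/.5 with baseline PDA and baseline mediator uncorrelated, the rates without adjustment are .014, .086 and .360.

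On precision, with no PDA–mediator link and a = b = .4, bootstrap power without versus with adjustment is .34 versus .40 if baseline PDA correlates .5 with 4-month PDA, .35 versus .35 at .3, and .32 versus .30 at 0.

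**The case against.** The strongest reply is that the plan has already discounted Aim 2d. It calls the analyses exploratory and underpowered and reads them as a pattern. At slopes of 0.1 to 0.2 the power gain is negligible, and intervals of about ±0.56 versus ±0.67 SD are both too wide to settle whether a small moderator effect exists. This stands, and it is why the point is minor. It does not justify the split: an acknowledged shortage of information is a reason not to discard more of it.

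A second reply is that the gain depends on linearity. This also stands. The plan gives no moderator distributions, and with 17 TAU patients a skewed moderator could give a few patients high leverage. The fix therefore needs a rule for skew and influence, and it must cover ordinal and multi-category moderators, which the all-binary rule at least handles.

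On mediation, silence is not exclusion: the covariate sentence does not say that nothing else will be entered. That too stands, so the request is to state it. The consistency argument would apply equally to the baseline of the family outcome in tests 4 to 6, which is not named either.

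Two stronger readings are tempting and are not supported:

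- A reader might take the 2/π result to mean that 51 patients act like 32. That is the large-sample limit; at this size and small slopes it is about 36 to 37.
- A reader might infer that tests 1 to 3 are invalid, because false positives on the b-path alone reach 6% to 22% in the assumed range (a from 0 to .2, baseline correlation .3), or 36% to 38% in the corner case. The planned test is the bootstrap of the product, and the plan uses b-path estimates by themselves only descriptively.

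**Conclusion.** The median split is a poorly motivated choice with a modest cost. Under linear moderation of a normal moderator it gives up about 27% to 29% of the information at small slopes (variance ratio .71 to .73). Continuous coding narrows the interval by about 16% and raises power noticeably only for moderate to large interactions. These figures rest on the assumed baseline correlation, alpha and linearity; the advantage vanishes or reverses in the non-linear cases shown. It would be wrong to infer that the split biases the trial's main comparison or inflates error in each moderator test. No confirmatory conclusion depends on Aim 2d. Severity: minor.

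The baseline PDA point is a secondary, optional matter of consistency and precision, not a demonstrated error. Clearly inflated false positives in the planned test appear only if the a-path is sizeable and baseline PDA is strongly related to both mediator and outcome (about 19% versus 4% to 5% at a = .4 and correlations .5/.5). In most milder settings they are near or below 5%. The documents supply none of these correlations. Adjustment would reduce confounding in a single-arm analysis, not remove it. Aim 2c is not covered by the exploratory caveat attached to Aim 2d, although the Aims section calls it a preliminary test.

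**What to change.** **Aim 2d.** Replace the median-split sentence with wording such as: *Continuous moderators will be entered as mean-centred continuous variables (transformed, e.g. log, if markedly skewed, with a check for influential observations) with a treatment-by-moderator product. Ordinal moderators will be entered as scores, and categorical moderators will be coded as binary or collapsed to categories fixed before analysis. Median splits will be used for display or sensitivity only.*

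Cost: no new data, only a change of coding and an influence check. It assumes a linear effect on the scale entered; retaining the split as a sensitivity analysis guards against a step-like effect.

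**Aim 2c (optional).** After the covariate sentence, add: *Tests 1–3, and the multiple-mediator follow-up model, will also include baseline PDA in the a and b models.*

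Cost: one degree of freedom per model and no new data, since drinking is already assessed at baseline (Baseline assessment; Form-90 in Table 1). If baseline PDA does not predict 4-month PDA, the loss is small (simulated bootstrap power .32 to .30 at a = b = .4).
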